- Compared to the control condition, does flexible internet-delivered exposure-based treatment lead to a larger improvement in symptom preoccupation, psychiatric symptom burden, and functional impairment? Hypothesis: Yes.
- In flexible internet-delivered exposure-based treatment, are effects maintained up to 12 months after treatment? Hypothesis: Yes.
- Is flexible internet-delivered exposure-based treatment cost-effective compared to the control condition? Hypothesis: Yes.
- Is the controlled effect of the flexible exposure-based treatment on self-rated somatic symptoms moderated by baseline symptoms and preoccupation? Hypothesis: Yes.
- Is the effect of the flexible exposure-based treatment on self-rated somatic symptom burden mediated by a reduction in symptom preoccupation? Hypothesis: Yes.

Methods

Design and power

Randomized controlled trial of flexible internet-delivered exposure-based treatment for distress related to somatic symptoms, based at Liljeholmen academic primary care clinic, Stockholm, Sweden. Patients (N=160) who report being bothered by somatic symptoms (and who may or may not meet criteria for a diagnosis where distress related to symptoms is common, such as fibromyalgia or asthma), who express interest in psychological treatment, and who's medical status does not make exposure therapy unsuitable are randomized (1:1), in consecutive even numbered cohorts, to flexible internet-delivered exposure-based treatment or an internet-delivered standardized education control. The trial is powered to enable the study of moderate between-group effects ($d=0.5$) as based on mean tests with 80% power, given $\alpha=0.05$ and up to 20% data loss.

Eligibility criteria

- a) (i) Either much bothered by at least one somatic symptom (2 points on at least one item of the PHQ-15) or at least a moderate overall somatic symptom burden (PHQ-15 sum 10 points (16)), with (ii) recurrent distress related to somatic symptoms ≥ 4 months
- b) Symptoms not best explained by, and clinical picture not dominated by, severe health anxiety (where an established treatment already exists (17)) or a non-somatoform psychiatric disorder such as depression, panic disorder, primary insomnia, or a chronic stress disorder
- c) Affirms that he or she is interested in completing an intense psychological treatment with the aim of reducing distress associated with physical symptoms
- d) Adult (≥ 18 years old)
- e) Living in Stockholm County
- f) Can read and write in Swedish

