After having completed the screening, applicants are contacted for a psychiatric assessment (primarily the MINI) and eligibility interview with a mental health clinician. As is routine practice at the clinic, this may be conducted face-to-face, via telephone, or via a secure video conferencing service. As is routinely done in the primary care clinic, the patient’s general practitioner is consulted whenever further medical evaluation is deemed necessary. Applicants who do not meet eligibility criteria a-k are excluded and referred to routine care, at the clinic if possible, and in accordance with regional healthcare guidelines. Applicants who meet eligibility criteria a-k are encouraged to complete the pre-treatment assessment. Those who do so are randomized (1:1) to flexible internet-delivered exposure-based treatment or the education control and are thereby included as participants in the trial. The subsequent 10 weeks constitute the main phase of the trial during which key measures are administered on a weekly basis (Table 1). At the end of the main phase follows the post-treatment assessment. Follow-up assessments follow 6 and 12 months after therapy.

Table 1. Key outcome measures and assessment points

Questionnaire	Outcome	Reference	SN	PRE	WK	POST	6MFU	12MFU
PHQ-15 (prim.)	Somatic symptoms	(16)	x	x	x	x	x	x
SSD-12	Symptom preoccupation	(20)	x	x	x	x	x	x
SYMPS-prel	Symptom preoccupation	Prel. version	x	x	x	x	x	x
GAD-7	Anxiety	(21)		x		x	x	x
PHQ-9 ^a	Depression	(22)	x	x		x	x	x
WHODAS 2.0	Disability	(23)	x	x		x	x	x
HAI-14	Health anxiety	(29)	x					
AUDIT, DUDIT	Alcohol, drug use	(30, 31)	x					
C/E scale	Credibility/expectancy	(24)			w. 3			
WAI-6	Relationship w. therapist	(25)			w. 3			
CSQ-8	Client satisfaction	(26)				x		
EQ-5D	Health-rel. quality of life	(27)		x		x	x	x
TIC-P	Resource use	(28)		x		x	x	x

12MFU = 12-month follow-up, 6MFU = 6-month follow-up, POST = post-treatment, PRE = pre-treatment (i.e., end of main phase), SN = screening, WK = weekly assessment (main phase week 1-9)

a) Suicidality item administered each week; patients contacted if flagged and referred to routine care as needed.

Data management

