The analysis plan here described will be pre-registered as part of this study protocol. Multiple imputation will be based on the following predictors: time, age, gender, screening somatic symptoms, screening symptom preoccupation, treatment adherence, and missing data rate. This will be done separately for each condition (exposure vs. control) so as to maintain group-specific interactions. Change in the primary outcome measure (PHQ-15) and other continuous scales will be analyzed using multilevel regression models (33) with patient at level 2, using an autoregressive (AR(1)) covariance structure, fitted by maximum likelihood. Longitudinal outcomes will be modelled intention-to-treat, with time, group (exposure vs. control), and the time \times group interaction as predictors ($\alpha=5\%$). As the feasibility trial was indicative of a curvilinear effect of time (unusual in the field), the inclusion of a time \times time interaction will also be considered based on model fit. The primary statistical test is that of the coefficient for the time \times group interaction pertaining to a group difference in average change in the PHQ-15 over the main phase of the trial, i.e., from pre- to post-treatment. Standardized mean effects are conceptualized as the time \times group interaction divided by the endpoint standard deviation. Long-term effectiveness is modeled using piecewise regression models, with a spline at post-treatment. Response rates are also explored in terms of clinically significant change (34). The following putative moderators will be explored based on time \times group \times moderator interactions: age, gender (if adequate power), screening somatic symptoms, and screening symptom preoccupation. Explorative secondary analyses will also focus on change in each somatic symptom domain of the PHQ-15 (pain, gastrointestinal, cardio-pulmonary, fatigue) as well as specific functional somatic syndromes and chronic health conditions if the number of patients in each condition is at least 5. Cost-effectiveness analysis is based on the incremental cost-effectiveness ratio (ICER) and focuses on a societal perspective, with resource use derived from the TIC-P and sensitivity analyses based on cluster bootstrapping (35). Mediation analysis is based on latent growth modelling (36), and random-intercepts cross-lagged panel models (37) to assess temporal superiority, i.e., whether change in putative mediators

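### The imputation predictors include no time × moderator terms, so under the natural reading the planned three-way moderator effects are modestly attenuated (about 7–18% at 20% loss)

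*Combined protocol and SAP*

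**What the plan says.** All of the relevant text is in the combined protocol and SAP. The separate SAP covers mediation and does not mention imputation.

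- **Imputation model** (Statistical analysis): "Multiple imputation will be based on the following predictors: time, age, gender, screening somatic symptoms, screening symptom preoccupation, treatment adherence, and missing data rate". These are single variables; no product terms are named.
- **Stratification** (same section): "This will be done separately for each condition (exposure vs. control) so as to maintain group-specific interactions".
- **Moderator tests** (same section): "The following putative moderators will be explored based on time" × group × moderator interactions. The moderators are "age, gender (if adequate power), screening somatic symptoms, and screening symptom preoccupation". All four are also on the imputation list.
- **Status of the question** (Key secondary research questions): "Is the controlled effect of the flexible exposure-based treatment on self-rated somatic symptoms moderated by baseline symptoms and preoccupation", with the hypothesis given as yes.
- **Analysis model** (Statistical analysis): multilevel regression "using an autoregressive (AR(1)) covariance structure, fitted by maximum likelihood". A time × time term may be added, depending on fit.
- **Occasions** (Table 1): PRE, POST and "WK = weekly assessment (main phase week 1-9"), which makes 11 main-phase time points.

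The plan does not state the data layout (long or wide), whether the imputation model has random effects, whether time is linear or categorical, or whether any analysis will be run without imputation.

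**The concern.** An imputation model should contain every association that the analysis model goes on to estimate. The plan accepts this principle, since its stated reason for imputing by arm is to keep group-specific interactions. The safeguard stops one term short. A three-way effect is the difference between arms in the time × moderator slope. If the model fitted within an arm has time and the moderator only as main effects, missing scores are filled in as though the rate of change did not depend on the moderator, or depended on it only as far as a patient's own observed scores pass that on. Mixing such values with observed ones pulls the three-way coefficient toward zero, and more imputations do not remove the pull. At stake is a key secondary question for which the investigators predict moderation.

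**Working it through.** **1. What 20% loss means in the plan.** Design and power gives d=0.5, 80% power, α=0.05 (two-sided assumed) and up to 20% data loss. The normal approximation gives 2 × (1.96 + 0.8416)² / 0.5² = 62.8, so 63 per arm. The t-test version gives 64 per arm, and 128 / 0.8 = 160, the stated N. The 20% is therefore most naturally patients lost to the mean comparison, that is, about 20% missing at POST. All three patterns below have 20% missing at POST.

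**2. What main-effects imputation does within an arm.** Scale time as t = 0, 0.1, …, 1 and let moderation at time t be δt per SD of moderator. A single-level fit with main effects of time and moderator, and missingness unrelated to outcome or moderator, gives a moderator coefficient of δ × t̄, where t̄ is the mean time of the observed records. An imputed value therefore carries δt̄ at every occasion instead of δt. Its slope moderation is zero, but a level difference remains. With an assumed δ = −0.30 and t̄ ≈ 0.48, an imputed POST value carries about −0.14. The simulation gave about −0.13 to −0.16.

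**3. Share of the three-way slope retained.** Let q be the fraction missing at time t. For an equally weighted straight-line slope,

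R = [S − A + t̄B] / S,

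where S = Σ(t − 0.5)t = 1.1, A = Σ(t − 0.5)qt and B = Σ(t − 0.5)q.

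| Pattern (assumed) | Records missing | t̄ | A | B | R |
|---|---|---|---|---|---|
| 20% of post-baseline records, intermittent | 18% | 0.489 | 0.220 | 0.100 | 0.84 |
| 20% of patients drop out, uniform over weeks | 10% | 0.478 | 0.220 | 0.220 | 0.90 |
| 20% of patients drop out in weeks 1–3 | 16% | 0.481 | 0.229 | 0.173 | 0.87 |

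First row: (1.1 − 0.220 + 0.489 × 0.100) / 1.1 = 0.84.

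**4. Other forms of imputation model.** The simulation used 11 occasions, a standardised moderator, a true three-way effect of −0.30 SD from PRE to POST, and imputation within arm. Monte Carlo SE was about 0.01–0.02. Share of the effect retained:

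| Pattern | Single-level | Random intercept | Random slope |
|---|---|---|---|
| Intermittent | 0.82 | 0.84 | 0.93 |
| Uniform dropout | 0.90 | 0.84 | 0.88 |
| Early dropout | 0.87 | 0.82 | 0.83 |

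The extremes, 0.93 and 0.82, give the 7–18% range. The single-level column agrees with step 3. With time × moderator added within arm, or with wide-format imputation, retention was 0.97–1.01.

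**5. Size against sampling error.** Take the planning precision: 128 analysed patients, a standardised moderator, unit-SD endpoint. The SE of a group × moderator coefficient is 2/√128 = 0.177. For the assumed effect of 0.30, the bias is 0.07 × 0.30 = 0.021 to 0.18 × 0.30 = 0.054, or 0.12 to 0.31 of a standard error. Power for 0.30 before any attenuation is Φ(0.30/0.177 − 1.96) ≈ 0.40.

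**The case against.** The strongest reply is that the plan lists predictors and not a model form. It does not say long format, linear time or single-level. Wide-format imputation gives each occasion its own coefficients and avoids the bias. This stands, and it makes the conclusion conditional. Even so, naming time as a predictor fits a long layout much better than a wide one, and random effects reduce the bias only in some patterns.

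The reply can add that the moderators are described as explored, that the trial is not powered for a three-way term, and that the bias works against the investigators' own hypothesis. All of this is right. It limits the importance of the point but does not remove it.

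The documents do not support four stronger readings that a reader might infer:

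- *Imputed records carry no moderation at all.* Imputing by arm keeps the group × moderator level difference, roughly half the true value at POST in the single-level case. Observed records keep all of theirs.
- *The imputation erases curvature.* The plan never says that time enters linearly, and time as a categorical occasion would keep curvature.
- *A quarter of the effect is lost.* Retention of 0.81 or 0.74 needs 30% or 40% missing at POST, above the 20% that reproduces N=160.
- *The primary result is biased.* Time is a predictor within each arm, so the missing moderator terms leave the time × group test alone.

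**Conclusion.** The point holds in conditional form. Followed as written in its natural reading, the predictor list omits the within-arm time × moderator terms that the planned three-way tests require. Those effects are then biased toward no moderation by roughly 7–18% at the planned loss.

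The range assumes missingness unrelated to outcome, the three patterns shown, and the variances and −0.30 SD effect chosen for the simulation. The closed-form check uses per-patient straight-line slopes and not the planned AR(1) model. The bias is at most about a third of a standard error at N=160, so sampling error dominates. It is still worth correcting, because it is systematic, it affects a key secondary question with a directional hypothesis, and the plan already intends its imputation to preserve interactions.

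**What to change.** State the imputation model in full: data layout, random effects and coding of time. Then choose one of the following.

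1. Within each arm, add time × age, time × gender, time × screening somatic symptoms and time × screening symptom preoccupation. If the analysis may use curvature, also add time × time or code time as a categorical occasion.
2. Impute in wide format within each arm.
3. Fit the moderator models by maximum likelihood to the observed data without imputation. The planned models already use maximum likelihood.

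The cost of the first option is a few extra terms in the code and slightly less stable imputation models with about 80 patients per arm. No data collection or design feature changes.

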### *Statistical analysis plan*

For this secondary mechanistic study, scoring of the PHQ-15 and SSS-12 will be informed by preceding psychometric evaluation of these scales, focusing on factor structures [16]. From the PHQ-15, items 4 (menstrual problems), 5 (headaches), 8 (fainting spells), and 11 (sexual pain/problems) will not be used for the sum score. The remaining 11 items, unlike the full 15 items, appears to have a stable structure and an important advantage is also that the general somatic symptom burden factor appears to explain just above 50% of the variance in these items, thus supporting simple sum scoring which is not always as straightforward [17]. From the SSD-12, item 7 (reassured by others) will not be used for the sum score. The remaining 11 items, unlike the full 12 items, appears to have a relatively stable, replicated, structure [18].

Prior to the main analyses, key variable distributions and correlations will be evaluated, and change over time visually inspected. Tests of hypotheses pertaining to mediation (Table 1) will then be based on parallel process growth curve models. This main analysis will proceed in three stages: First, models with a random intercept and slope will be built to capture unconditional growth in each of the putative mediators and outcomes. Second, each putative mediator will be entered into the same model as the corresponding outcome, and tests for within-group mediation will concern the slope of the potential mediator (the a-path in the traditional Baron & Kenny mediation framework [19], assuming time to be the independent variable) multiplied by the effect of this slope on the slope of the outcome (equivalent to the b-path in the traditional Baron & Kenny mediation framework, assuming time to be the independent variable). Third, a variable for allocation (exposure therapy vs. healthy lifestyle promotion; 1/0) will be entered and tests for between-group mediation will concern the path from this variable, to the slope of the potential mediator, to the slope of the outcome. All tests of mediation will be bootstrapped (2000 samples) [20].

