The annual societal cost of medically unexplained symptoms in Sweden is approximately 40 billion SEK (1), i.e., similar to the annual cost of cancer (2). Prevalent chronic diseases like asthma and diabetes are also commonly associated with somatic symptoms that lead to significant distress and pervasive behavioral changes that result in functional impairment and place added strain on the health care system. Exposure-based treatment, where the patient willingly engages with stimuli that give rise to unwanted physical sensations or distress, has shown promise in reducing somatic symptom load and increasing quality of life in several conditions where patients commonly report substantial distress related to somatic symptoms, such as in asthma (3), musculoskeletal pain (4), and functional gastrointestinal syndromes (5). In routine care, however, access to such exposure-based treatment is limited. One reason for this is probably that there exists no flexible exposure-based treatment protocol that can be easily tailored to suit a wide spectrum of patient groups who suffer from distress related to recurrent somatic symptoms. In a recent single group feasibility trial (N=33) at Karolinska Institutet, Sweden, we found that such a tailored exposure-based treatment delivered in an online text-based format can be acceptable, with high treatment adherence, adequate treatment satisfaction, large and lasting within-group improvement, and no serious adverse events. This is a randomized controlled trial (N=160) where we aim to test if the same tailored internet-delivered exposure-based treatment is more efficacious than a standardized education control for adult patients with clinically significant distress related to somatic symptoms in a primary care setting. Primary outcome is change in self-rated somatic symptom burden as modelled using linear mixed models fitted on weekly Patient Health Questionnaire 15 sum scores over the treatment period. Long-term efficacy is assessed up to one year after treatment and cost-effectiveness is investigated based on the incremental cost-effectiveness ratio. We expect this trial to be of notable clinical importance as it will be indicative of the usefulness of a broad exposure-based treatment protocol for distress related to somatic symptoms in primary care.

Overview of the field (background)

Recurrent distress associated with somatic symptoms: a common and costly problem

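### The primary time-by-group test names AR(1) as its only covariance and does not state the random effects or a robust standard error; the two literal readings err in opposite directions if patients differ in rate of change

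*Combined protocol and SAP*

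**What the plan says.** In the combined protocol and SAP, the Statistical analysis section specifies "multilevel regression models (33) with patient at level 2, using an autoregressive (AR(1)) covariance structure, fitted by maximum likelihood". The fixed effects are time, group and their interaction, and the interaction coefficient from pre- to post-treatment is the primary test. Only a time-by-time term is left to model fit. The opening summary describes the primary outcome as "change in self-rated somatic symptom burden as modelled using linear mixed models fitted on weekly Patient Health Questionnaire 15 sum scores". By Table 1, the main phase has a pre-treatment score, nine weekly scores and a post-treatment score, so 11 occasions.

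Missing data are multiply imputed first, and of that step the plan says: "This will be done separately for each condition (exposure vs. control) so as to maintain group-specific interactions".

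Nothing else in the documents completes the covariance statement for this test:
- The cluster bootstrap in the same section is for the cost-effectiveness analysis.
- The separate mediation SAP says that "models with a random intercept and slope will be built to capture unconditional growth in each of the putative mediators and outcomes", but this concerns the mediation models, which use an 11-item PHQ-15 score. Its later mention of the primary publication's models does not give their random effects.

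The protocol does expect patients to respond differently. A key secondary question reads: "Is the controlled effect of the flexible exposure-based treatment on self-rated somatic symptoms moderated by baseline symptoms and preoccupation? Hypothesis: Yes". The moderators to be explored are "age, gender (if adequate power), screening somatic symptoms, and screening symptom preoccupation", entered through three-way interactions in exploratory analyses and not in the primary model.

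**The concern.** The covariance sentence can be fitted in at least two literal ways. The summary's reference to linear mixed models, together with patient at level 2, points to a random intercept plus AR(1) residuals. AR(1) alone also fits the words.

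Within an arm, a random intercept plus AR(1) treats all patients as sharing one underlying slope. If true rates of change vary, that variation belongs in the standard error of the slope difference, and this model captures it only in part. AR(1) alone makes the opposite error: it treats stable differences in level as slowly decaying correlation and so overstates the uncertainty of the slope.

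This coefficient decides the trial. A plan that allows models with different error rates leaves the choice open until the data have been seen, which is what pre-registration is meant to prevent.

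**Working it through.** **1. The plan's own figure.** For d = 0.5, 80% power, α = 0.05 (two-sided assumed) and 20% loss, the normal approximation gives 2 × (1.96 + 0.8416)² / 0.5² = 62.8, so 63 per arm. Then 63 / 0.8 = 78.75, so 79 per arm and 158 in total. The exact t-test needs 64 per arm, and 64 / 0.8 = 80 gives the stated 160. This is a mean test, so the covariance question does not affect it.

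**2. Inputs.** From the documents: 80 per arm, times 0 to 10 weeks, α = 0.05, loss up to 20%. Assumed, because no variance components are given: the intercept and residual variances, the residual autocorrelation and the SD of true 10-week change.

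**3. One worked case.** Take intercept SD 4, residual SD 2, autocorrelation 0 and change SD 2 (slope SD 0.2 per week).
- Sum of squared times about week 5: 2 × (1 + 4 + 9 + 16 + 25) = 110.
- True variance of one patient's slope: 4/110 + 0.2² = 0.0364 + 0.0400 = 0.0764.
- True SE of the 10-week difference: 10 × √(2 × 0.0764 / 80) = 0.437.
- SE reported by the best-fitting random intercept plus AR(1) covariance, found numerically: 0.345.
- Ratio 0.345 / 0.437 = 0.79, so type I error = 2Φ(−1.96 × 0.79) = 12.2%.

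Adding a random slope returns the reported SE to 0.437 and the error to 5.0%.

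**4. Complete data, large sample.** Assumed: total SD 5, residual variance 6, straight-line differences between patients. Type I error of random intercept plus AR(1):

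| Autocorrelation | change SD 1 | 1.5 | 2.5 | 4 |
|---|---|---|---|---|
| 0 | 6.5% | 8.2% | 12.4% | 17.2% |
| 0.3 | 5.9% | 6.8% | 9.3% | 12.2% |
| 0.6 | 5.5% | 6.0% | 7.1% | 8.0% |

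With no slope variance it is 5.0%. For AR(1) alone, the ratio of reported to true SE is 1.13 to 2.27. At the lower end, 2Φ(−1.96 × 1.13) = 2.7%, which is the maximum.

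**5. With imputation by arm.** Simulation used 80 per arm, 20% dropout completely at random, 20 imputations, two forms of imputation model and 4000 null replicates per scenario (Monte Carlo SE 0.3–0.5 points).

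| Change SD | Random intercept + AR(1), type I error |
|---|---|
| 0 | 4.2–4.5% |
| 1 | 4.8–5.6% |
| 1.5 | 4.9–5.8% |
| 2.5 | 6.0–8.7% |
| 4 | 6.8–12.8% |

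A common time-by-time term made no difference (5.8 against 5.8%, and 7.3 against 7.4%). AR(1) alone gave 0–2.5%, with power of 75–90% at d = 0.5. A random-slope model that switched to a clustered robust standard error when the slope variance was near zero held 4.2–6.0% for change SD 1–4, with power of 94–100%. Not simulated: dropout related to outcome; adherence, age and gender as imputation predictors; group-specific curvature.

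**6. Patient-specific curvature.** In the setting of step 4 (complete data), individual curves with a mid-treatment SD of 2 points were added. Type I error of random intercept plus AR(1) at autocorrelation 0, 0.3 and 0.6 became:
- change SD 1: 4.2, 3.7, 3.1%
- change SD 1.5: 5.6, 4.5, 3.5%
- change SD 2.5: 9.3, 6.6, 4.5%

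**7. Efficiency of keeping random intercept plus AR(1).** The fault lies in the reported SE and hardly at all in the estimate. With intercept SD 3.5, residual SD 2.5, autocorrelation 0.5 and change SD 4, the true SE of its estimate is 0.818, against 0.813 for the random-slope model. The loss is 0.818 / 0.813 − 1 = 0.6%.

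**The case against.** The case for leaving the text alone has four parts.

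- **The text is incomplete, not wrong.** A multilevel model with patient at level 2 may include a random slope. This stands: a reader might infer that the plan rules one out, and it does not.
- **The direction is not general.** The protocol reports a curvilinear time effect in the feasibility trial. That describes the mean curve, but individual curves may differ too, and step 6 shows that this can remove or reverse the understatement. This also stands. It is not correct to say that random intercept plus AR(1) is anti-conservative whenever patients differ.
- **The size may be negligible.** Under the planned imputation, type I error at change SD 1–1.5 is within the range seen for the random-slope rule. Nothing in the documents places the trial at 2.5 or above. The moderation hypothesis supports some slope variation but says nothing about its amount. This stands.
- **The other reading is safe.** AR(1) alone is conservative, and its simulated power of 75–90% lies around the 80% design target. That is true, but it was 4–25 points below the random-slope rule in the same data.

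What remains is that the wording allows models with different error rates for the deciding test, and no other section settles which applies. That holds whatever the variances are.

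**Conclusion.** The point holds as an under-specified variance model, with a conditional effect on the error rate. If patients differ mainly in linear rate of change, random intercept plus AR(1) tends to understate the standard error and AR(1) alone overstates it. With imputation by arm, the excess over 5% is negligible at a change SD of 1–1.5 points. It is modest to material at 2.5 (6.0–8.7%) and 4 (6.8–12.8%).

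A reader might infer from step 4 that the true type I error is 12–17%. The documents do not support this: those values need complete data, large slope variance and little autocorrelation, and no variance component is reported. They also do not support concluding that the standard error is certainly too small, because the intended random effects are not stated and marked individual curvature can offset the effect. The change is a cheap improvement to the primary analysis, not the correction of a demonstrated error.

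**What to change.** In the Statistical analysis section of the combined protocol and SAP, state one variance rule for the primary test before the data are analysed, and apply it in every imputed dataset before pooling.

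- **Simplest:** random intercept plus AR(1) residuals, always with a patient-clustered robust standard error. With about 160 patients this should be approximately calibrated whether or not slopes or curves vary. It was not itself run through the imputation simulation.
- **Alternative:** random intercept and random slope for time with AR(1) residuals as the primary model, and the clustered robust version as a prespecified sensitivity analysis.

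A rule that changes estimator whenever any one imputed dataset shows near-zero slope variance is best avoided. In simulation with 20 imputations this happened in 26–68% of trials at change SD 1 and 17–49% at 1.5, so imputation noise would often choose the primary analysis.

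The cost is one or two sentences and no new data. When slopes vary, the confidence interval is wider than the model-based one from random intercept plus AR(1). For change SD 1–4 in large samples the increase is 2–12% at autocorrelation 0.6, 4–27% at 0.3 and 6–43% at 0. The simulated power cost at d = 0.5 was 0–2 points for the random-slope rule in step 5. The sample size does not change.

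### The primary model freely estimates an arm difference at a pre-treatment score taken before randomisation, and so gives up some precision; the planned test remains valid.

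*Combined protocol and SAP*

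**What the plan says.** All references are to the combined protocol and SAP unless stated.

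- **Order of events (Procedure).** "Applicants who meet eligibility criteria a-k are encouraged to complete the pre-treatment assessment", and then "Those who do so are randomized (1:1) to flexible internet-delivered exposure-based treatment or the education control". Eligibility criterion l also requires a complete pre-treatment assessment. The Table 1 legend glosses PRE as the end of the main phase. That conflicts with the Procedure text and reads as a labelling slip.
- **Scores (Table 1).** The PHQ-15 is taken at screening, PRE, weekly ("WK = weekly assessment (main phase week 1-9") and POST. PRE to POST is therefore 1 + 9 + 1 = 11 scores, with a separate screening score before them.
- **Primary model (Statistical analysis).** "Longitudinal outcomes will be modelled intention-to-treat, with time, group (exposure vs. control" and their interaction. The covariance is AR(1) with patient at level 2, fitted by maximum likelihood. A time-by-time term may be added on model fit. The coding of time is not given.
- **Primary test.** The coefficient for "a group difference in average change in the PHQ-15 over the main phase of the trial, i.e., from pre- to post-treatment". PRE is therefore one of the modelled outcomes.
- **Screening PHQ-15.** It is named as an imputation predictor and an exploratory moderator, not as a covariate in the primary model.
- **Sample size (Design and power).** "Patients (N=160) who report being bothered by somatic symptoms" are to be randomised. The target is a difference of d = 0.5 between the arms, and the calculation is described in these words: "as based on mean tests with 80% power, given $\alpha=0.05$ and up to 20% data loss".

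**The concern.** PRE is completed before allocation, so the two arms have the same expected PRE mean. A model with free group and time-by-group terms estimates a PRE difference already known to be zero. That holds under any coding of time. The estimated PRE difference is correlated with the estimated difference in slope, so its sampling error carries into the primary coefficient. Setting the difference to zero removes that part of the error.

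What is at stake is the width of the primary confidence interval. Every patient already supplies the PRE score, because a complete one is a condition of entry.

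**Working it through.** **1. The plan's own figure.** For d = 0.5, two-sided alpha 0.05 (sidedness assumed) and 80% power, n per arm = 2(1.960 + 0.842)²/0.5² = 62.8, so 63. Allowing for 20% loss, 63/0.8 = 78.75, so 79 per arm or 158 in total. The t-test version needs 64 per arm, 128 in total, and 128/0.8 = 160. The stated N reproduces. It uses no baseline correlation and no repeated measures.

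**2. Two-score form.** With equal variances σ², pre-post correlation r and n per arm:

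- Change-score contrast (free PRE difference): 4σ²(1 - r)/n
- Common PRE mean: 2σ²(1 - r²)/n
- Ratio: (1 + r)/2

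For r = 0.4, 0.5, 0.6, 0.7 and 0.8 the ratio is 0.70, 0.75, 0.80, 0.85 and 0.90.

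**3. Eleven-score form.** Let t = 0, 0.1, ..., 1, let Z = [1, t], and let V be the within-patient covariance matrix. With n per arm, the variance of the slope difference is

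- free PRE difference: (2/n) × the slope element of (Z'V⁻¹Z)⁻¹
- common PRE mean: (2/n) / (t'V⁻¹t)

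The second cannot exceed the first.

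A case that can be done by hand is a random intercept with autocorrelation 0 and total variance 1. Here Σ(t - mean)² = 1.1, Σt² = 3.85 and (Σt)² = 5.5² = 30.25. For intercept share s, the ratio is 1.1 / [3.85 - 30.25 × s/((1 - s) + 11s)].

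- s = 0.7: 30.25 × 0.7/8.0 = 2.647; 1.1/1.203 = 0.914
- s = 0.5: 30.25 × 0.5/6.0 = 2.521; 1.1/1.329 = 0.828

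The other settings were computed numerically with 80 per arm and complete data. All correlations are assumed.

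| Assumed structure | Variance ratio, common / free PRE mean |
|---|---|
| Random intercept + AR(1), share 0.5-0.7, autocorrelation 0-0.7 | 0.745-0.914 |
| Random slopes added (SD 3-4 points over 10 weeks, PRE SD 5 points), intercept-slope correlation -0.5 | down to about 0.60 |
| Same, correlation 0 | 0.82-0.97 |
| Same, correlation +0.3 | 0.92-1.00 |

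Without random slopes, √0.914 = 0.956 and √0.745 = 0.863, so the interval is about 4-14% narrower.

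**4. Screening score.** This used a separate set of assumptions: intraclass correlation 0.4-0.75, autocorrelation 0-0.6, slope SD 0-0.8 of the PRE SD, intercept-slope correlation 0 or -0.3, and screening 3 weeks before PRE. Ratios are against the planned model.

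- Screening main effect, group left free: 1.000 in every setting
- Screening and screening-by-time, group left free: 0.94-1.00
- Common PRE mean alone: 0.64-0.98
- Common PRE mean plus screening and screening-by-time: 0.61-0.94

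**5. Form of the mean.** In the no-random-slope settings (share 0.5, 0.6, 0.7; autocorrelation 0, 0.3, 0.5, 0.7), against the planned linear coefficient:

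- Quadratic mean with group interactions and a common PRE mean, PRE-to-POST difference: 0.77-0.92
- Visit-specific POST contrast with a common PRE mean: 0.79-1.87, and above 1 in 7 of 12 settings

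**6. Power.** In the same settings, at a difference of 0.5 PRE SD with 80 per arm and complete data, the planned model has about 91% to over 99% power. With a common PRE mean it has about 97% to over 99%. With 20% loss the low end of the planned model is about 83%. With random slopes (SD 0.6-0.8 of the PRE SD) the planned model has 74-98%.

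**The case against.** The strongest reply is that nothing is broken. Randomisation makes the planned time-by-group test unbiased, its standard error already covers chance imbalance at PRE, and N = 160 reproduces. All of that stands. A reader might infer that chance imbalance or regression to the mean biases the estimate. The documents do not support that, because regression to the mean is equal in expectation across arms.

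The gain may also be negligible. That stands where the intercept-slope correlation is positive. The documents give no intraclass correlation, autocorrelation or slope variance, and the random intercept is itself inferred from patient being at level 2. The direction is certain; the size is not.

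Three further stronger readings are tempting:

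- **80% power becomes 83-90%.** That applies the variance ratios to a power figure from a two-sample mean test, not from the 11-score model. Planned-model power is often well above 80% already.
- **Omitting the screening score costs precision in its own right.** As a main effect in the planned model it gains nothing, and with its time interaction very little. It helps mainly on top of a common PRE mean.
- **A visit-by-visit mean would serve equally well.** Its POST contrast is less precise than the planned coefficient in most settings examined.

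A common starting point could also distort a straight-line slope if change is curved, and the plan reports curvature in the feasibility trial. With no treatment effect both arms follow the same curve, so this is not a route to false positives. The quadratic term deals with the rest.

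Finally, the plan was to be pre-registered. The separate mediation SAP gives N = 161 and describes the week-3 ratings in the past tense, so recruitment appears complete. This limits what should be done now.

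**Conclusion.** The point holds as one of efficiency only. PRE precedes randomisation, the primary model leaves the arm difference at PRE free, and removing that freedom cannot raise the variance of the primary coefficient. Under the assumed random intercept plus AR(1) the variance falls by 9-25%. With random slopes the fall is about 0-40%, depending mainly on the intercept-slope correlation. These ranges rest on assumed correlations and complete data, and should be quoted as such. Neither the validity of the planned test nor the stated sample size is in question, and no figure for this trial's gain in power follows from the documents.

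**What to change.** In the Statistical analysis section:

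1. State that time is coded 0 at PRE, and drop the group main effect so that both arms share one PRE mean. Keep the time-by-group difference in change from PRE to POST as the primary test.
2. If the time-by-time term is included, keep the common PRE mean and add the group interaction with the quadratic term. The primary quantity is then the arm difference in change at POST implied by both interactions. Do not move the primary test to a visit-specific contrast.
3. Optionally add screening PHQ-15 and its interaction with time, on top of the common PRE mean, for a further and usually modest gain. Do not add it only as a main effect to the present model.

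The cost is a small change to a pre-registered model, with no new data. If the primary analysis has already been run, leave the registered test as primary and report this model as a labelled sensitivity analysis.
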